5.4.1. Individual Safety Stopping Rules

Study medication will be discontinued in the event of any of the following:

- If a subject experiences a serious or severe clinically significant AE that in the clinical judgement of the investigator, after consultation with the medical monitor, there is a reasonable possibility that the AE is related to investigational product.
- The subject becomes pregnant.
- The subject initiates treatment with any prohibited medication for the treatment of PsO as listed in Section 6.11.2.
- The subject develops a serious opportunistic or atypical infection.
- If the liver chemistry stopping criteria (Section 5.4.3), QTc stopping criteria (Section 5.4.4), or haematologic stopping criteria (Section 5.4.5) are met.

- The subject experiences any signs of suicidal ideation or behaviour (Section 7.3.7).

5.4.2. Group Safety Stopping Rules

In addition to the criteria specified above, AEs, SAEs, laboratory abnormalities, ECG abnormalities and changes in vital signs occurring across all randomised subject will be regularly reviewed by the Sponsor Safety Review Team (SRT) in order to ensure appropriate subject safety. Any changes to the study due to safety reasons will be promptly communicated to the appropriate Regulatory Authorities.

[figure not shown]
5.4.3. Liver Chemistry Stopping Criteria

Liver chemistry stopping and increased monitoring criteria have been designed to assure subject safety and evaluate liver event etiology (in alignment with the FDA premarketing clinical liver safety guidance).

<http://www.fda.gov/downloads/Drugs/GuidanceComplianceRegulatoryInformation/Guidances/UCM174090.pdf>

Figure 3 Phase II Liver Chemistry Stopping and Increased Monitoring Algorithm

Phase II Liver Chemistry Stopping and Increased Monitoring Algorithm

Liver Safety Required Actions and Follow up Assessments Section can be found in [Appendix 2](#).

5.4.3.1. Study Treatment Restart or Rechallenge

Study treatment restart or rechallenge after liver chemistry stopping criteria are met by any subject participating in this study is not allowed.

5.4.4. QTc Stopping Criteria

A subject who meets either of the bulleted criteria below will be withdrawn from the study:

- QTc >500 msec or Uncorrected QT >600 msec
- Change from baseline of QTc >60 msec

For patients with underlying **bundle branch block**, follow the discontinuation criteria listed below:

Baseline QTc with Bundle Branch Block	Discontinuation QTc with Bundle Branch Block
<450 msec	>500 msec
450–480 msec	≥530 msec

- The *same* QT correction formula *must* be used for *each individual subject* to determine eligibility for and discontinuation from the study. This formula may not be changed or substituted once the subject has been enrolled.
- For example, if a subject is eligible for the protocol based on QTcB, then QTcB must be used for discontinuation of this individual subject as well.
- Once the QT correction formula has been chosen for a subject's eligibility, the *same formula* must continue to be used for that subject *for all QTc data being collected for data analysis*. Safety ECGs and other non-protocol specified ECGs are an exception.
- The decision to withdraw a subject will be based on an average QTc value of triplicate ECGs. If an ECG demonstrates a prolonged QTc, obtain 2 more ECGs over a brief period (5-10 minutes), and then use the averaged QTc values of the 3 ECGs to determine whether the subject should be discontinued from the study.

5.4.5. Haematologic Stopping Criteria

Study treatment will be stopped for a subject if any of the following haematological stopping criteria is met:

- Haemoglobin <9 g/dL or an absolute decrease of ≥3 g/dL from baseline (pre-dose Day 1)
- Platelets <50 × 10⁹/L

5.5. Subject and Study Completion

A completed subject is one who has completed all phases of the study including the follow-up visit.

The end of the study is defined as the last subject's last visit.

6. STUDY TREATMENT

6.1. Investigational Product and Other Study Treatment

The term 'study treatment' is used throughout the protocol to describe any combination of products received by the subject as per the protocol design. Study treatment may therefore refer to the individual study treatments or the combination of those study treatments.

Study Treatment		
Product name:	GSK2982772	Placebo
Dosage form:	Tablet	Tablet
Unit dose strength(s)/Dosage level(s):	30 mg	NA
Route of Administration	For oral use only	For oral use only
Dosing instructions for Cohort 1:	Take TWO tablets in the MORNING and TWO tablets in the EVENING as directed	Take TWO tablets in the MORNING and TWO tablets in the EVENING as directed
Dosing instructions for Cohort 2:	Take TWO tablets THREE times daily as directed by your physician	Take TWO tablets THREE times daily as directed by your physician
Physical description	White to almost white, round, film coated tablet	White to almost white, round film coated tablet
Source of procurement	Study medication is supplied by GlaxoSmithKline	Placebo is supplied by GlaxoSmithKline

6.2. Treatment Assignment

At screening, a unique Subject Number will be assigned to any subject who has at least one Screening procedure performed, other than informed consent. The unique Subject Number will be used to identify individual subjects during the course of the study.

Subjects who meet screening eligibility criteria will be randomised to a treatment group through Interactive Response Technology System (IRTS). The IRTS will confirm the subject's CRF number (Subject Number) and provide the randomisation number, where:

- A randomisation number will be assigned from a randomisation schedule generated by Clinical Statistics, prior to the start of the study, using validated internal software. Once assigned, this number must not be reassigned to any other subject in the study.

The randomisation is centrally controlled by the IRTS.

In Cohort 1, subjects will take study medication every day, twice a day, approximately 12 hours apart. Subjects will be randomised to receive either GSK2982772 or placebo in a 2:1 ratio. In Cohort 2, subjects will take study medication every day, three times a day, with approximately 8 hours between each dose. Subjects will be randomised to receive either GSK2982772 or placebo in a 3:1 ratio.

Subjects will be administered the first daily dose of study medication by site staff during the site visit for Day 1 (week 0) and Day 43 (week 6). Subjects will self-administer all other doses of study medication and will record the date and time in the diary cards provided to them.

6.3. Planned Dose Adjustments

No dose adjustments are allowed.

6.4. Blinding

This will be a double blind (sponsor unblind) study and the following will apply.

- Sponsor unblinded refers only to the Data Review Committee (DRC) consisting of the GSK Project Physician Lead (PPL), the study statistician, the study pharmacokineticist, Pattern Recognition Receptor (PRR) Discovery Performance Unit (DPU) Head, the Early Development Leader (EDL), the Safety Review Team (SRT) leader, or their designees on an ongoing basis. A physician external to the GSK2982772 project team may also be involved in the data review. A data review charter will identify the specific GSK individuals involved; outline in detail the activities of this review, and how the integrity of the study will be maintained. The rest of the core GSK study team will remain blinded.
- The investigator or treating physician may unblind a subject's treatment assignment **only in the case of an emergency** OR in the event of a serious medical condition when knowledge of the study treatment is essential for the appropriate clinical management or welfare of the subject as judged by the investigator. Investigators have direct access to the subject's individual study treatment.
- It is preferred (but not required) that the investigator first contacts the Medical Monitor or appropriate GSK study personnel to discuss options **before** unblinding the subject's treatment assignment.
- If GSK personnel are not contacted before the unblinding, the investigator must notify GSK as soon as possible after unblinding, but without revealing the treatment assignment of the unblinded subject, unless that information is important for the safety of subjects currently in the study.
- The date and reason for the unblinding must be fully documented in the CRF.
- A subject will be withdrawn if the subject's treatment code is unblinded by the investigator or treating physician. The primary reason for discontinuation (the event or condition which led to the unblinding) will be recorded in the CRF.
- GSK's Global Clinical Safety and Pharmacovigilance (GCSP) staff may unblind the treatment assignment for any subject with an SAE. If the SAE requires that an expedited regulatory report be sent to one or more regulatory agencies, a copy of the report, identifying the subject's treatment assignment, may be sent to investigators in accordance with local regulations and/or GSK policy.

6.5. Packaging and Labeling

The contents of the label will be in accordance with all applicable regulatory requirements.

6.6. Preparation/Handling/Storage/Accountability

No special preparation of study treatment is required.

- Only subjects enrolled in the study may receive study treatment and only authorized site staff may supply or administer study treatment. All study treatments must be stored in a secure environmentally controlled and monitored (manual or automated) area in accordance with the labelled storage conditions with access limited to the investigator and authorized site staff.
- The investigator, institution, or the head of the medical institution (where applicable) is responsible for study treatment accountability, reconciliation, and record maintenance (i.e. receipt, reconciliation and final disposition records).
- Further guidance and information for final disposition of unused study treatment are provided in the SRM.
- Under normal conditions of handling and administration, study treatment is not expected to pose significant safety risks to site staff.
- A Material Safety Data Sheet (MSDS)/equivalent document describing occupational hazards and recommended handling precautions either will be provided to the investigator, where this is required by local laws, or is available upon request from GSK.

6.7. Compliance with Study Treatment Administration

When subjects are dosed at the site, they will receive study treatment directly from the investigator or designee, under medical supervision. The date and time of each dose administered in the clinic will be recorded in the source documents. The dose of study treatment and study subject identification will be confirmed at the time of dosing by a member of the study site staff other than the person administering the study treatment.

When subjects self-administer study treatment(s) at home, compliance with GSK2982772 will be assessed through querying the subject during the site visits and documented in the source documents (diary cards) and CRF. A record of the number of GSK2982772 or placebo tablets dispensed to and taken by each subject must be maintained and reconciled with study treatment and compliance records. Treatment start and stop dates, including dates for treatment delays and/or dose reductions will also be recorded in the CRF.

6.8. Treatment of Study Treatment Overdose

For this study, any dose of GSK2982772 >120 mg daily will be considered an overdose in Cohort 1 and any dose of GSK2982772 >180 mg daily will be considered an overdose in Cohort 2. GSK does not recommend specific treatment for an overdose. The investigator will use clinical judgement to treat any overdose as and when they are made aware of this.

In the event of an overdose the investigator or treating physician should:

1. Contact the Medical Monitor immediately.

2. Closely monitor the subject for adverse events (AEs)/serious adverse events (SAEs) and laboratory abnormalities until GSK2982772 can no longer be detected systemically (at least 2 days for GSK2982772).
3. Obtain a plasma sample for pharmacokinetic (PK) analysis if requested by the Medical Monitor (determined on a case-by-case basis)
4. Document the quantity of the excess dose as well as the duration of the overdosing in the CRF.

Decisions regarding dose interruptions or modifications will be made by the investigator in consultation with the Medical Monitor based on the clinical evaluation of the subject.

6.9. Treatment after the End of the Study

Subjects will not receive any additional treatment from GSK after completion of the study because other treatment options are available.

The investigator is responsible for ensuring that consideration has been given to the post-study care of the subject's medical condition, whether or not GSK is providing specific post-study treatment.

6.10. Lifestyle and/or Dietary Restrictions

- Subjects must adhere to the contraceptive requirements listed in [Appendix 5](#).
- Subjects must abstain from alcohol for 24 hours before all clinic visits.

6.10.1. Sun Exposure and Activity

Subjects must not sunbathe or use a tanning device (sun bed or solarium) for 14 days prior to Day 1 until the follow up visit (Day 112). Subjects will be advised that when they are outdoors they should wear protective clothing (e.g. sun hat, long sleeves) covering the selected target lesions for biopsy and PLSS scoring as well as use a broad spectrum UVA/UVB sunscreen and lip balm (SPF ≥ 30) on exposed areas when outdoors.

Subjects will abstain from strenuous exercise for 48 hours prior to each blood collection for clinical laboratory tests.

6.11. Concomitant Medications and Non-Drug Therapies

6.11.1. Permitted Medications and Non-Drug Therapies

Selected medications for the treatment of PsO may be taken, with specific requirements listed in [Table 1](#), and as long as they are not prohibited (Section [6.11.2](#)). All concomitant medications taken during the study will be recorded in the CRF. The minimum requirement is that drug name and dates of administration are recorded.

Table 1 Specific Requirements for Permitted Medications During the Study

Therapy	Requirement
Emollients (excluding those containing salicylic acid)	Omit on day of study visits until after all skin assessments have been performed. May be used at other times.
Medicinal shampoos that contain tar and/or salicylic acid (but not corticosteroids)	Permitted at any time on scalp area.

6.11.2. Prohibited Medications and Non-Drug Therapies

Table 2 lists prohibited medications for defined periods of time before and during the study until after the follow up visit (Day 112).

Subjects who start prohibited medications or therapies as a treatment for PsO or other reasons during the study may be withdrawn from study treatment for safety reasons. If in any doubt, investigators are advised to discuss medications with the medical monitor.

Table 2 Prohibited Medications

Therapy	Time period
Biologic therapies for the treatment of chronic plaque-type psoriasis 
 Exception: Can have only been exposed to one anti-TNF biologic previously administered in a clinical study setting. 	12 weeks or 5 half-lives (whichever is longer) prior to first dose. Otherwise, cannot have been on an anti-TNF biologic treatment at any time during the study.
Photochemotherapy with psoralens and ultraviolet A (PUVA) therapy	4 weeks prior to first dose until after the follow up visit (Day 112).
Phototherapy (e.g., UVB or self treatment with tanning beds)	14 days
Topical therapies (e.g., corticosteroids, cyclosporine, calcineurin inhibitors, coal tar, vitamin A or D analog preparations, anthralin, calcipotrienen, retinoids, tazarotene, methoxsalen, trimethyl psoralens).	2 weeks prior to first dose until after the follow up visit (Day 112).
Systemic immunomodulating medications for other medical conditions that are known to affect psoriasis, including but not limited to oral corticosteroids cyclosporine, methotrexate, cyclophosphamide, and beta-adrenergic blockers.	4 weeks prior to first dose until after the follow up visit (Day 112).
Intravenous or oral calcineurin inhibitors (e.g., tacrolimus).	
P-glycoprotein (Pgp) inhibitors including but not limited to amiodarone, azithromycin, captopril, carvedilol, clarithromycin, conivaptan, cyclosporine, diltiazem, dronedarone,	4 weeks prior to first dose until after the follow up visit (Day 112).

Therapy	Time period
erythromycin, felodipine, itraconazole, ketoconazole, lopinavir, ritonavir, quercetin, quinidine, ranolazine, ticagrelor, verapamil [FDA, 2012].	
Narrow therapeutic index (NTI) CYP3A4 substrates including but not limited to alfentanil, astemizole, cisapride, cyclosporine, dihydroergotamine, ergotamine, fentanyl, pimozide, quinidine, sirolimus, tacrolimus, terfenadine [FDA, 2012].	4 weeks prior to the first dose until after the follow up visit (Day 112).
Live vaccination	Vaccinations (either live, attenuated) are not permitted within 30 days of randomization or plan to receive a vaccination during the study until follow-up visit. If indicated, non-live vaccines (e.g. inactivated influenza vaccines) may be administered whilst receiving GSK2982772 based on an assessment of the benefit: risk (e.g. risk of decreased responsiveness). Investigators are expected to follow local and/or national guidelines with respect to vaccinations, including against pneumococcus and influenza, in subjects with PsO.

7. STUDY ASSESSMENTS AND PROCEDURES

Protocol waivers or exemptions are not allowed with the exception of immediate safety concerns. Therefore, adherence to the study design requirements, including those specified in the Time and Events Table (Section 7.1), are essential and required for study conduct.

Supplementary study conduct information not mandated to be present in this protocol is provided in the SRM. The SRM will provide the site personnel with administrative and detailed technical information that does not impact subject safety.

This section lists the procedures and parameters of each planned study assessment. The exact timing of each assessment is listed in the Time and Events Table Section 7.1.

The following points must be noted:

- If assessments are scheduled for the same nominal time, THEN the assessments should occur in the following order:
 - a. Patient Reported Outcomes (PROs)
 - b. 12-lead ECG
 - c. vital signs

d. blood draws

Note: The timing of the assessments should allow the blood draw to occur at the exact nominal time.

- The timing and number of planned study assessments, including safety, pharmacokinetic, pharmacodynamic/biomarker or other assessments may be altered during the course of the study based on newly available data (e.g., to obtain data closer to the time of peak plasma concentrations) to ensure appropriate monitoring.
- The change in timing or addition of time points for any planned study assessments must be documented in a Note to File which is approved by the relevant GSK study team member and then archived in the study sponsor and site study files, but this will not constitute a protocol amendment.
- No more than 500 mL of blood will be collected over the duration of the study, including any extra assessments that may be required.
- The Institutional Review Board/ Independent Ethics Committee (IRB/IEC) will be informed of any safety issues that require alteration of the safety monitoring scheme or amendment of the Informed Consent Form.

A table defining the allowed variance in timings of assessments without being considered a protocol deviation will be included in the Study Reference Manual (SRM).

7.1. Time and Events Table

Procedures	Screening	Treatment Period												Early Withdrawal ¹⁴	Follow Up	Notes	
		Day 1	Day 8	Day 15	Day 22	Day 29	Day 36	Day 43 (week 6)	Day 50	Day 57	Day 64	Day 71	Day 78				
Screening Procedures																Visit windows Screening: up to 30d before Day 1. Treatment Period (except Day 1 & 85): ± 3d. Day 1 NA; Day 85 ± 2d. Early Withdrawal: NA Follow Up: 28d after last dose ± 3d	
Site Visit	X	X	X	X		X		X		X		X		X	X		
Phone call					X		X		X		X		X				
Safety Assessments																1. Full physical exam: height/weight at Screening, height not required at later timepoints. 2. Vitals: BP, HR, RR, temperature. ECG triplicate at Screening only. 3. Urinalysis not required on Days 29, 57 and 71. 4. If urine test is positive, confirmatory serum test must be performed. 5. Pre-dose 6. In Cohort 1, subjects must take study medication twice a day approx. 12h apart. In Cohort 2, subjects must take study medication three times a day approx. 8h apart. Exact time of dosing to be recorded in diary cards. On Days 43 and 85, subjects must not take medication at home in the morning. Subjects will complete pre-dose assessments and then will be administered their morning dose of medication at site on Day 43 only. On Day 85, subjects no longer dosed. 7. Diary card checked by site staff and new diary card dispensed at every study visit. 8. Blood samples for inflammatory	
Full physical exam ¹	X													X	X	X	
Brief physical exam		X ⁵		X		X		X ⁵		X		X					
12-lead ECG, vital signs ²	X	X ⁵	X	X		X		X ⁵		X		X		X	X	X	
Columbia Suicide Severity Rating Scale (C-SSRS)	X	X ⁵						X ⁵						X	X		
Hematology, chemistry, urinalysis	X	X ⁵	X	X		X ³		X ⁵		X ³		X ³		X	X	X	
FSH & estradiol (if applicable)	X																
Serum pregnancy (WCBP)	X																
Urine pregnancy test (WCBP only) ⁴			X ⁵	X	X		X		X ⁵		X		X	X	X		
Study Treatment																	
Randomisation		X															
Study medication ⁶		X	X														
Dispensing of study medication		X				X				X							
Dispensing of diary cards ⁷	X	X	X		X		X		X		X		X				
PROs/ Disease Assessments																	

Procedures	Screening	Treatment Period												Early Withdrawal ¹⁴	Follow Up	Notes
		Day 1	Day 8	Day 15	Day 22	Day 29	Day 36	Day 43 (week 6)	Day 50	Day 57	Day 64	Day 71	Day 78	Day 85 (week 12)		
Psoriatic Body Surface Area	X	X ⁵												X	X	
PASI, PGA, PLSS, Itch	X	X ⁵		X		X		X ⁵		X		X		X	X	
DLQI	X	X ⁵						X ⁵						X	X	
Photograph of lesions		X ⁵						X ⁵						X	X	
Other Assessments and Procedures																
Blood sample for inflammatory biomarkers ⁸		X ⁵						X ⁵						X	X	
Blood sample for mRNA analysis ⁸		X ⁵						X ⁵						X	X	
Blood sample for Target Engagement		X ⁵						X ⁵						X	X	
PK blood samples ⁹		X						X ⁵						X	X	
Skin punch biopsies for PK, inflammatory biomarkers, mRNA, target engagement & pathway engagement		X ^{5,10}						X ¹¹						X ¹²		
Pharmacogenetic sample (PGx)		X ¹³														
Con med review & AE/SAE reporting			X-----X													

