3. OBJECTIVE(S) AND ENDPOINT(S)

Objectives	Endpoints
Primary	

 To investigate the safety and tolerability of 60 mg twice daily doses, and 60 mg three times daily doses, of GSK2982772 in subjects with active plaque-type psoriasis. 	
 Adverse events Clinical laboratory values (clinical chemistry, haematology and urinalysis) Vital sign measurements (blood pressure, heart rate, respiratory rate and body temperature) 12-Lead ECG monitoring
Secondary	

 To investigate the pharmacokinetics of GSK2982772 in blood following 60 mg twice daily doses, and 60 mg three times daily doses, of GSK2982772 in subjects with active plaque-type psoriasis. 	
 Pre-dose plasma concentrations of GSK2982772 at Days 43 (Week 6) and 85 (Week 12). Post-dose plasma concentrations of GSK2982772 on Days 1 and 43 (Week 6) at 1, 2, 4 and 6 hours post dose.

 To investigate the effect of 60 mg twice daily doses, and 60 mg three times daily doses, of GSK2982772 on inflammatory biomarkers in skin biopsies from psoriatic skin lesions in subjects with active plaque-type psoriasis. 	
 Change from baseline in histopathological scoring of psoriatic lesional biopsies which may include, but are not limited to the following as data permit: K16, CD3/CD11c, CD161, elastase positive dermal cells and epidermal thickness. mRNA expression of inflammatory gene transcripts which may include, but are not limited to the following as data permit: IL-4, IL-10, IL-17, IL-21, IL-22, IL-23, TNF and IFNy on Days 1 (Week 0) and 43 (Week 6).

 To investigate the effect of 60 mg twice daily doses, and 60 mg three times daily doses, of GSK2982772 on disease activity in subjects with active plaque-type psoriasis 	
 Percentage change from baseline and actual Psoriatic Lesion Severity Sum (PLSS) scores in the index lesion.
Exploratory	

 To investigate the effect of 60 mg twice daily doses, and 60 mg three times daily doses, of GSK2982772 on disease activity in subjects with active plaque-type psoriasis 	
 Change from baseline in Psoriasis Area Severity Index (PASI) scores. The proportion of subjects who achieve PASI \geq 50%, 75%, and 90% improvement from baseline score.

Objectives	Endpoints

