4.5. Dose Justification

The initial selection of the 60 mg BID dose being tested in this study is based on the safety, PK, and PD data from the GSK2982772 First Time in Human (FTiH) study, 200975. GSK2982772 administered at 60 mg BID for 14 days was well tolerated and no safety concerns were identified. A BID dosing regimen was initially selected over a QD dosing regimen due to the short half-life of GSK2982772 in humans (~2 hours). Based on preliminary PK/PD modelling of ex-vivo RIP1 target engagement and GSK2982772 concentrations from the multiple dose ascending part of Study 200975, a 60 mg BID dose was predicted to have on average 95% RIP1 target engagement in blood and approximately 90% of subjects are predicted to have >90% RIP1 target engagement in blood at C_{min} using a novel in-house ex-vivo PD/target engagement assay based solely on the TNF pathway which is believed to be a key component of the RIP1 pathway. Assuming a skin: blood ratio of 0.4 (as observed in the rat), the average RIP1 target engagement in skin is predicted to be 92%. At C_{min} , 44% of subjects are predicted to have >90% RIP1 target engagement in the skin and 90% of subjects are predicted to have >80% RIP1 target engagement in the skin.

However, based on final PK/PD modelling from the full repeat dose part of the Study 200975 (up to 120 mg BID), a 60 mg BID dose is now predicted to have on average 99% RIP1 target engagement in blood and approximately 90% of subjects will have >85% target engagement at C_{min} . In skin, assuming the same skin: blood ratio of 0.4 as noted

above, the average RIP target engagement at 60 mg BID in skin is predicted to be 96%. At C_{min} , 43% of subjects are predicted to have >90% RIP1 target engagement in the skin and 90% of subjects are predicted to have >70% RIP1 target engagement in the skin.

In review of this final FTiH data, it is believed that the C_{min} target exposure may not be achieved with a 60mg BID dosing regimen. The C_{min} values at 60 mg TID are predicted to be approximately 3.5 fold higher than for 60 mg BID. Therefore, a 60 mg TID cohort is now being proposed.

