Respiratory	
Non-clinical data: In the single dose Safety Cardiovascular and Respiratory Study in monkeys, a decrease in minute volume (MV) and respiratory rate was observed at all doses (10, 100, and 300 mg/kg). These findings were noted to be reversible and mild in severity. In a 14 day repeat oral dose respiratory function study, no respiratory effects on respiratory function (e.g., tidal volume, minute volume or respiratory rate) were observed at doses of 1 or 10 mg/kg/day. See Investigator's Brochure for GSK2982772 [GlaxoSmithKline Document Number 2014N204126_01].
 
Clinical data: In the FTiH study, repeat doses of GSK2982772 were administered x 14 days in 36 healthy male volunteers. Extensive respiratory monitoring with end-tidal CO₂ (ETCO₂), oxygen saturation (SpO₂) and nocturnal respiratory
	
Subject Monitoring:
 
 Subjects should be monitored for standard respiratory-related adverse events. Vital signs will be monitored during study visits.

Potential Risk of Clinical Significance	Summary of Data/Rationale for Risk	Mitigation Strategy
	rate monitoring was performed. No SAEs occurred, and no drug-associated respiratory-related adverse events were identified.	
CNS/Suicidality	
GSK2982772 is considered to be a CNS-active drug based on pre-clinical studies.
 
Clinical data: In the FTiH study, there have been some reports of lethargy, abnormal dreams, and depressed mood. No events of suicidal ideation or behaviour or changes in behaviour were reported.
	
Subject selection:
 
 Subjects with a current history of Suicidal Ideation Behaviour (SIB) as measured using the Columbia Suicide Severity Rating Scale (C-SSRS) or a history of attempted suicide will be excluded from the study. 
Subject Monitoring:
 
 Subjects should be monitored appropriately and observed closely for suicidal ideation and behaviour or any other unusual changes in behaviour. Baseline and treatment emergent assessment of suicidality will be conducted by trained site personnel using the Columbia Suicide Severity Rating Scale (C-SSRS) in all subjects. See Section 7.3.7.

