7.3.5. Electrocardiogram (ECG)

- Triplicate ECGs will be obtained at screening and single 12-lead ECGs will be obtained at every other time point during the study using an ECG machine that automatically calculates the heart rate and measures PR, QRS, QT, and QTc (F or B) intervals. Refer to Section [5.4.4](#) for QTc withdrawal criteria and additional QTc readings that may be necessary.
- ECG is to be measured in a supine or semi supine position after 5 minutes rest.

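### No scheduled ECG or vital-sign reading, both primary safety endpoints, is tied to a post-dose time, so none can be paired with a measured peak concentration

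*Protocol*

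**What the plan says.** Section 3 of the Protocol lists among the primary safety endpoints "Vital sign measurements (blood pressure, heart rate, respiratory rate and body temperature") and "12-Lead ECG monitoring". A secondary endpoint in the same section is "Post-dose plasma concentrations of GSK2982772 on Days 1 and 43 (Week 6) at 1, 2, 4 and 6 hours post dose".

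Section 7 refers to the Time and Events Table (Section 7.1) for the exact timing of every assessment. The row "12-lead ECG, vital signs" cites only notes 2 and 5, and note 5 means pre-dose. It is attached to Days 1 and 43. Note 6 withholds the home morning dose on Days 43 and 85 only. For Day 43 it says: "Subjects will complete pre-dose assessments and then will be administered their morning dose of medication at site on Day 43 only". For Day 85 it says that dosing has ended.

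Section 7.3.5 adds that, after triplicates at screening, "single 12-lead ECGs will be obtained at every other time point during the study". Neither that section nor Section 7.3.4 on vital signs gives a time after dosing. Section 4.5 explains the initial choice of twice-daily over once-daily dosing as "due to the short half-life of GSK2982772 in humans (~2 hours").

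**The concern.** With a half-life this short, concentration swings widely within each dosing interval. An effect on QTc, heart rate, blood pressure or respiratory rate that follows plasma concentration would be largest in the first hours after a dose and smallest just before the next. The schedule fixes its dose-related readings at that low point. It leaves unused the two visits at which dosing is supervised and concentrations are measured for 6 hours.

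Peaks are not a remote worry in this programme. The Amendment 2 rationale (Section 12.6.2) presents a lower peak-to-trough ratio as desirable for safety and tolerability. The risk table (Section 4.6.1) records that in a single-dose monkey study "a decrease in minute volume (MV) and respiratory rate was observed at all doses", and it names vital signs at study visits as part of the monitoring. At stake is whether the ECG and vital-sign displays can say anything reliable about peak exposure, and whether any reading can be set against a measured peak concentration.

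**Working it through.** **Step 1. Treatment-period visits, from Section 7.1 (row entries with notes 5 and 6).**

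| Visit | ECG and vital signs | Dosing that day |
|---|---|---|
| Day 1 | pre-dose | first dose at site; plasma at 1, 2, 4, 6 h |
| Days 8, 15, 29, 57, 71 | no time relative to dose | home dose not withheld |
| Day 43 | pre-dose | home dose withheld, dose then given at site; plasma at 1, 2, 4, 6 h |
| Day 85 | off-dose | home dose withheld, none given |

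Readings fixed to a post-dose time: 0. Some notes to the table are cut off in the available text, but this row cites only notes 2 and 5.

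**Step 2. Reproduce the plan's own exposure figures (Section 4.5).** AUC ratio, three times versus twice daily: 9.9/6.6 = 1.50, as stated (50% higher). Cmax ratio: 0.80/0.70 = 1.14 (stated as about 10%). For the stated 3.5-fold Cmin ratio, one-compartment steady state with k = ln 2 / half-life gives

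ratio = [e^(−8k)/(1 − e^(−8k))] / [e^(−12k)/(1 − e^(−12k))].

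At 2 h: (0.0625/0.9375)/(0.015625/0.984375) = 4.2. At 2.25 h it is 3.65, and at 2.5 h it is 3.28. The value 3.5 is reached at 2.34 h, which is compatible with a half-life of about 2 h, so the simple model is adequate here.

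**Step 3. Trough as a share of peak, instantaneous absorption.** Share = 2^(−interval/half-life). At 2 h: 2^(−6) = 1.6% (12 h interval) and 2^(−4) = 6.3% (8 h interval).

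**Step 4. The same with oral absorption.** The documents give no absorption rate or Tmax, so first-order absorption with ka from 0.7 to 3 per hour is assumed. With τ the dosing interval, C(t) is proportional to

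e^(−kt)/(1 − e^(−kτ)) − e^(−ka·t)/(1 − e^(−ka·τ)).

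Trough is C(τ) and peak is the maximum over the interval.

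| Half-life | Trough/peak, twice daily | Trough/peak, three times daily | Time of peak |
|---|---|---|---|
| 1.5 h | 0.6–2.4% | 4.1–13.4% | 0.7–1.7 h |
| 2.0 h | 2.3–6.0% | 9.3–21.9% | 0.8–2.0 h |
| 2.5 h | 5.0–10.6% | 15.1–29.8% | 0.8–2.1 h |
| 3.0 h | 8.3–15.6% | 20.8–36.6% | 0.9–2.2 h |

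At the stated half-life the Day 43 reading is therefore taken at about 2–6% of peak in Cohort 1 and 9–22% in Cohort 2. Across half-lives of 1.5 to 3 h the ranges widen to about 1–16% and 4–37%. The modelled peak falls around the existing 1 h and 2 h plasma draws.

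**The case against.** The strongest reply is that five of the seven visits after Day 1 follow a home dose that is not withheld. With 20 + 18 = 38 subjects on active treatment and full attendance, that is 38 × 5 = 190 readings, against 38 × 2 = 76 on Days 43 and 85. Dose times are entered in diary cards, so time since dose can be worked out afterwards. This stands. A reader might infer that no reading is taken after a dose, or that a peak-related effect would go unseen and be reported as absent. The documents support neither: some of those readings may well fall near peak. They do so only by chance, however, with self-recorded dose times and without the post-dose sampling profile. How to tabulate them by time since dose is analysis-plan detail and is not criticised here.

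A reader might also take the monkey finding as a sign of an unmonitored hazard. Section 4.6.1 does not support that. It describes the effect as mild and reversible, reports no respiratory effect in a 14-day repeat-dose study at 1 or 10 mg/kg/day, and reports no drug-associated respiratory events in 36 repeat-dosed volunteers under extensive monitoring. Section 4.5 places the predicted three-times-daily exposure well within that observed at 120 mg twice daily, and the risk table lists no QTc or haemodynamic risk. These points lower the urgency but do not supply the reading in patients.

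Low concentration is also not the same as low pharmacological effect. Section 4.5 predicts that about 90% of subjects on 60 mg twice daily exceed 85% target engagement in blood at Cmin. On-target effects would largely persist at trough, so the point concerns effects that follow plasma concentration.

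Finally, the protocol tests no formal safety hypothesis and claims no exposure–QTc analysis. Section 7 already lets timings move towards peak by a Note to File if new data suggest it. The schedule is thus internally consistent, and the issue was foreseen. An option that depends on new data is still not a scheduled assessment.

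**Conclusion.** The point holds as a cheap improvement to the design, not as an error or a contradiction. No ECG or vital-sign reading is fixed to a post-dose time. The readings with a controlled time since dose are uninformative about peak-related effects, and none can be paired with a measured peak concentration. That conclusion follows from the table alone.

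Its size rests on the stated half-life of about 2 h and on an absorption rate that the documents do not give. On those terms the Day 43 reading sits at roughly 2–6% of peak twice daily and 9–22% three times daily. The three-times-daily figure is the less certain: the half-life that reproduces the plan's own Cmin ratio is 2.34 h, which lies between the 2.0 h and 2.5 h rows of the table and pushes the range upwards.

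**What to change.** In Section 7.1, preferably keep the Day 43 pre-dose ECG and vital signs, which match the Day 1 pre-dose baseline like for like. Add one further single ECG and vital-signs set just before the 1 h or 2 h post-dose plasma draw on Day 43. The order in Section 7 (ECG, vital signs, then blood at the exact nominal time) already accommodates this.

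If no extra set is wanted, re-time the existing Day 43 set to that draw and rely on Day 85 for the off-dose comparison.

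Costs: a few minutes of site time at a visit where plasma is already drawn to 6 h, or the loss of the Day 43 pre-dose reading if the set is moved. The skin biopsies are taken pre-dose under local anaesthetic on the same day (Sections 4.4 and 7.6.1) and may add noise to heart rate and blood pressure. The placebo arm has the same biopsies and shares that noise. The change concerns the timing of assessments only and leaves dosing and the stopping rules as they are.
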